Ancestry Informative Markers. For Hispanic participants, a set of 106 SNPs that discriminate indigenous American, African, and European ancestry (also known as ancestry informative markers or AIMs) will be used to estimate the proportion of genetic ancestry in study participants. The SNPs chosen maximize information for more than one ancestral population pairing, with a large difference in allele frequency between ancestral populations and the ancestry informative markers are widely spaced throughout the genome and have a well-balanced distribution across all 22 autosomal chromosomes. Genotyping will be done using a multiplex PCR coupled with single base extension methodology with allele calls using a Sequenom analyzer.

FUNDING for RESEARCH

American Cancer Society – Research Scholar Grant

Pilot study funding – U54 PSM-MCC partnership

Main project funding – U54 PSM-MCC partnership

CITED REFERENCES

- Armstrong, B. K. and A. Kricker (1993). "How much melanoma is caused by sun exposure?" Melanoma Res **3**(6): 395-401.
- Aspinwall, L. G., J. M. Taber, S. L. Leaf, W. Kohlmann and S. A. Leachman (2013). "Genetic testing for hereditary melanoma and pancreatic cancer: a longitudinal study of psychological outcome." Psychooncology **22**(2): 276-289.
- Azzarello, L. M., S. Dessureault and P. B. Jacobsen (2006). "Sun-protective behavior among individuals with a family history of melanoma." Cancer Epidemiol Biomarkers Prev **15**(1): 142-145.
- Azzarello, L. M. and P. B. Jacobsen (2007). "Factors influencing participation in cutaneous screening among individuals with a family history of melanoma." J Am Acad Dermatol **56**(3): 398-406.
- Berrigan D, Dodd K, Troiano RP, Reeve B, Ballard-Barbash R (In Press). "Associations between Language Acculturation of Adult Hispanics in the United States and Physical Activity." Research Quarterly for Exercise and Sport, In Press.
- Berwick, M., C. B. Begg, J. A. Fine, G. C. Roush and R. L. Barnhill (1996). "Screening for cutaneous melanoma by skin self-examination." J Natl Cancer Inst **88**(1): 17-23.

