For our H/L populations living in Tampa Bay and Puerto Rico, we propose and intervention study in which we will recruit and randomize 800 H/L participants, 400 of whom we are considered at high risk and 400 of whom are considered at the average risk based on *MC1R* genotyping to receive standard risk and prevention information or to receive precision risk and prevention information based on *MC1R* testing results. Of the total 800 subjects, 400 H/L subjects will be identified from scheduling records of the Family Medicine and General Internal Medicine clinics of the Morsani Center at the University of South Florida, and 400 we will be recruited by our colleagues at the Ponce Health Sciences University in Ponce, PR. Therefore, a total recruitment for H/L at each site will be 400 subjects with 200 whom are considered at average risk and 200 whom are considered at high risk based on *MC1R* genotyping test results.

RESEARCH PROCEDURES

Summary. Participants in this study will be white, non-Hispanic patients with an appointment to see a physician in the Departments of Family Medicine and General Internal Medicine at the primary care clinics of the University of South Florida Health Morsani College of Medicine. We plan to approach approximately 18,500 clinic patients over a 30 month period. We will screen patients for study eligibility based on responses to questions about skin phenotypes, early detection behaviors, and past history of melanoma, and anticipate enrolling 1200 eligible study participants all of whom will sign informed consent. For our H/L population study participants will be patients with an appointment to see a physician in the Departments of Family Medicine and General Internal Medicine at the primary care clinics of the University of South Florida Health Morsani College of Medicine. Based on our ongoing recruitment, nearly 10% of

participants report being H/L. Participants (n=400) will be recruited prospectively at their clinic visit over an 18-month period.

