Consented patients with *MC1R* genotypes not selected for randomization. We will randomly select only 500 white, non-Hispanic participants from each of the *MC1R* risk categories (low and high) to participate further in our study. Therefore, some participants may receive a letter from the research team thanking them for their interest in our research project and informing them that they were not selected for further study participation. The letter will inform patients about their *MC1R* risk status and provide educational materials highlighting standardized information for the general population about melanoma, melanoma risk, melanoma prevention (i.e. sun protection and skin examination), and sun protection behaviors for children.

Randomization. For our white, non-Hispanic population we will randomize 500 participants with high risk and 500 participants with low risk *MC1R* genotypes. 50% of high risk and low risk individuals will be randomly allocated to the intervention and placebo arm (250 participants per arm) using permuted blocks, with a block size of four, and equal weighting scheme.

For our H/L population we will randomize 200 participants with high risk and 200 participants with low risk *MC1R* genotypes, with 50% of high risk and average risk individuals will be randomly allocated to the intervention and placebo arm (100 participants per arm).

Because our prior work does not indicate an increased risk of melanoma associated with low risk *MC1R* genotypes, we focus our study hypothesis on the intervention effect among persons with high risk *MC1R*. However, analysis of the efficacy of the intervention among participants in the low risk *MC1R* genotype group will enable us to assess any potential negative impact upon prevention behaviors that feedback of a 'negative' genetic test results may produce. Moreover, because the health educator will be blinded to the *MC1R* genotype status of participants randomized to the placebo arm, the addition of the low risk group affords implicit control of potential bias introduced by the health educator's knowledge of participant *MC1R* status at the time of the education session.

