For Aim 2, the outcome of interest for this aim is having a skin examination (yes/no) assessed at the 6- and 12-month follow-up visits for our white, non-Hispanic population and at 3 and 9 month follow-up visits for our H/L population. This outcome will be a composite of examinations performed by a clinician (e.g. primary care doctor or dermatologist; Section A, Q11) or those completed by oneself or one’s partner (i.e. self-skin examination; Section A, Q13). We will tailor the suggested text of Q11 and Q13 given in Glanz et al. to fit our Aim and our timeline (Glanz et al. 2008). Q11 will be revised to read “In the past [time] months, have you had ...” (compared to “Have you ever had ...” as it currently reads). We will tailor the timeframe to correspond to the baseline, 6 or 12 month survey for our white, non-Hispanic population and at 3 or 9 month survey for our H/L population: at baseline the timeframe will be “in the past 12 months”; at the 6 and 12 month follow-up surveys, the timeframe will be “in the past 6 months” for our white, non-Hispanic population and “in the past 3 months” for our H/L population. In order to address the potential of a ceiling effect, we will ask participants who respond ‘yes’ to having had a skin examination in the past 6 months (white, non-Hispanic population) and 3 months (for our H/L population) the month and year of examination and whether the examination occurred at the Morsani Family Medicine or General Internal Medicine clinics. The outcome will be operationalized such that responding ‘yes’ to questions regarding completion of a skin examination by a clinician or by oneself or one’s partner will be considered a ‘yes’ response for skin examinations. Thus, this outcome is operationally a binary response (e.g., yes/no in the past 6 months (for our white, non-Hispanic participants) and in the past 3 months (for our H/L participants)) measured at the 6- and 12-month follow-up visits for our white, non-Hispanic population and at 3 and 9 month follow-up visits for our H/L population.

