Aim 1. We will use a linear GEE regression model with main effects for the intervention (standard risk and prevention plus genetic education versus standard risk and prevention education only), time, and the interaction terms between the intervention and time. The interaction term will be the main test of interest as it assesses average departure from the slope due to the intervention. We will include other covariates related to dropout or involving potential baseline imbalances between the intervention groups as appropriate, as well as month of completion of the questionnaires to account for seasonality.

We will perform analyses to test whether participants and eligible non-participants differ on basic demographic variables using cross-sectional logistic or linear regression models for binary or continuous factors, respectively. We will perform attrition analyses to determine whether participants and dropouts differ on key variables. We will include these factors in the above ITT model to see if they affect the results. A few randomly missing observations have only a slight impact on power and do not introduce bias. However, large numbers of non-randomly missing values can bias results.

We also will conduct mediator analyses to determine whether the effect of the intervention on prevention behaviors is explained by health beliefs or cancer distress. We will use a series of models to examine whether (a) the intervention is predictive of the mediator, (b) the mediator is predictive of prevention behaviors in a multivariable model controlling for the intervention, and (c) the addition of the mediator to a

multipredictor model for prevention behaviors attenuates the estimated coefficient for the intervention. To assess mediation effects, we will use the approaches by Imai et al., which are available through add-on packages to existing statistical software (such as R and STATA) (Imai et al. 2010, Imai et al. 2012). Similar to the method of Preacher and Hayes (Preacher et al. 2008), their methods employ bootstrapping to estimate mediating causal effects . These analyses will be used to estimate the direct effect of the intervention via pathways other than through the posited mediator, its indirect effect via the mediator, and the degree of mediation. This approach will allow us to quantify the effect of the intervention due to the potential mediator (if any), which can inform future interventions or prevention strategies.

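### The H/L trial runs equally at two sites, but the plan states no site stratum or blocking for its randomisation and prespecifies no site term in its models

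*Combined protocol and SAP*

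**What the plan says.** All references are to the combined protocol and SAP.

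- **Quotas (Project Description).** The H/L trial has 800 participants, 400 from Tampa Bay clinics and 400 "recruited by our colleagues at the Ponce Health Sciences University in Ponce, PR". The section adds that "a total recruitment for H/L at each site will be 400 subjects with 200 whom are considered at average risk" and the other 200 at high risk.
- **Sample size (Statistics, Hispanic/Latino study population).** It counts 400 high-risk participants, 200 from each site, and 200 per arm.
- **Allocation (Research Procedures, Randomization).** "For our H/L population we will randomize 200 participants with high risk and 200 participants with low risk" genotypes, with half of each risk group "randomly allocated to the intervention and placebo arm (100 participants per arm"). Site is not mentioned. The white, non-Hispanic trial is allocated "using permuted blocks, with a block size of four, and equal weighting scheme"; no such statement is made for H/L.
- **Models (Statistics, Aims 1 and 2).** GEE models contain intervention, time and their interaction, and the interaction is the main test. Covariates tied to dropout or baseline imbalance may be added where judged appropriate, "as well as month of completion of the questionnaires to account for seasonality". Site is not named, and no result by site is planned.
- **Follow-up question (Primary Outcome of the Study, Aim 2).** Participants reporting an examination give its month and year, and say "whether the examination occurred at the Morsani Family Medicine or General Internal Medicine clinics".

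**The concern.** Sites in different locations, with different clinics and recruiting teams, can plausibly differ on both primary outcomes: midday hours outdoors, and whether a skin examination took place. Where recruitment is fixed at half per site, one expects site to be a stratification factor and a model term. The plan commits to neither, and its allocation counts do not fit its own totals.

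At stake are the efficiency of the two primary H/L comparisons, the ability to reconstruct how participants were allocated, and a prespecified view of whether the intervention worked in both places. One month-of-completion effect pooled over two locations would not capture a seasonal pattern that differs between them.

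**Working it through.** **1. The counts side by side**

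| Section | High risk | Average/low risk | Total | High risk per arm |
|---|---|---|---|---|
| Project Description, trial-wide | 400 | 400 | 800 | not given |
| Project Description, per site | 200 | 200 | 400 | not given |
| Statistics, H/L power | 400 | not given | not given | 200 |
| Randomization | 200 | 200 | 400 | 100 |

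The Randomization row equals the per-site row. It is either a per-site allocation that does not say so, or a trial-wide count that contradicts the other two sections.

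**2. The plan's own power figure**

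The H/L Aim 1 effect is printed as d = 30 and read here as 0.30. Two-sided alpha of 0.05 is stated for the white, non-Hispanic trial and assumed for H/L. For one visit, n per arm = 2(1.960 + 0.842)²/0.30² = 175. Power is Φ(0.30/√(2/n) − 1.96):

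- 200 per arm: 85.1%.
- 160 per arm (the 20% attrition given under H/L Aim 2): 76.5%.

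The stated 80% falls between these and is not reproduced exactly. That is a separate matter; the two figures serve only as reference values below.

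**3. Size of a chance imbalance if allocation ignores site**

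Take 400 high-risk participants, 200 per site and 200 per arm. The number from Ponce in one arm is hypergeometric, with SD = √(200 × 0.25 × 200/399) = 5.0 and a 95% range of 90 to 110. The difference in site share between arms has SD 2 × 5.0/200 = 5 percentage points. For a site gap of g SD, the arm difference at one visit moves with SD 0.05g. That is 0.01 to 0.04 SD for g = 0.2 to 0.8, against a target of 0.30.

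**4. Cost for a single-visit comparison**

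The documents give no site difference, so g is assumed. With two equal sites, omitting site multiplies the estimated standard error by f = √(1 + g²/4).

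| g | f | Power, 160 per arm, site adjusted | Unadjusted, allocation ignores site: Φ(2.683/f − 1.96) | Unadjusted, allocation within site: Φ(2.683 − 1.96f) | Actual level of a 5% test, allocation within site |
|---|---|---|---|---|---|
| 0.2 | 1.005 | 76.5% | 76.1% | 76.2% | 4.9% |
| 0.5 | 1.031 | 76.5% | 74.0% | 74.6% | 4.3% |
| 0.8 | 1.077 | 76.5% | 70.2% | 71.6% | 3.5% |

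Here 2.683 = 0.30/√(2/160). At 200 per arm, 85.1% falls to 84.7%, 82.9% and 79.5% when allocation ignores site.

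**5. The planned Aim 1 test**

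Intervention by time is a within-person contrast, so a constant site gap subtracts out. A simulation used baseline and two follow-ups, 200 per arm, an assumed correlation of 0.5 and 8,000 runs per setting. Power for the change-from-baseline contrast was about 93% at g = 0, 0.5 and 1.0, with or without site stratification. Adding a site difference of 0.3 SD that appears only at follow-up left it at 92.5% to 93.2%. Without stratification, type I error was 4.7% to 5.4% for the change and single-visit contrasts.

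**6. Aim 2**

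H/L patients examined in the past year are excluded (Research Procedures; Selection of Subjects), and the baseline question covers the past 12 months. The baseline outcome is therefore essentially no for everyone at both sites. Baseline cannot absorb a site difference, so the test is in effect a follow-up comparison.

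The H/L power section gives a control rate of 15% to 35%. Assume, for scale, that the sites sat at the two ends. The mean within-site variance is (0.15 × 0.85 + 0.35 × 0.65)/2 = 0.1775 and the pooled variance is 0.25 × 0.75 = 0.1875. Then f = √(0.1875/0.1775) = 1.028, and the gap is 0.20/√0.1775 = 0.47 SD. This extreme of the plan's own range is close to the g = 0.5 row.

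**The case against.** The strongest reply is that the Randomization counts fit the other sections only if read per site. The H/L enrolment target of 400 under Consent Process, drawn from the local clinics, supports that reading. Allocation would then already be balanced within site. This stands: a reader might infer that the randomisation ignores site, but the text does not establish it. What remains is that the stratum and block scheme are unstated, and that stratified allocation analysed without site gives conservative tests.

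Second, the models admit covariates for baseline imbalance. That is true, but inclusion depends on judgement after seeing the data, and site is not named.

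Third, a reader might infer bias, or two separate harms from imbalance and from between-site variance. Neither follows. Participants are individually randomised, so the comparison remains unbiased and type I error is not inflated. Under unstratified allocation, the imbalance and the extra variance are one cost.

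Fourth, a reader might apply the single-visit loss to both primary tests. For Aim 1 that fails, because a constant gap cancels. Only differences that change with time or season remain. They are possible: recall covers 12 months at baseline and 3 months at H/L follow-up, and season may act differently in the two places.

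Finally, the follow-up question is not useless at Ponce. Month and year can be used there, and the yes/no outcome does not depend on where the examination took place.

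**Conclusion.** The point holds as a gap in specification with a modest statistical cost. Site is stated neither as a stratum nor as a model term, and the H/L counts in Project Description, Randomization and Statistics must be reconciled.

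For follow-up comparisons at 160 per arm, the loss is about 2 to 6 percentage points of power for site gaps of 0.5 to 0.8 SD, and negligible at 0.2 SD. These gaps are assumptions. Aim 2 is exposed to this loss. Aim 1 is exposed only to site differences that vary over time, and the simulated effect of a 0.3 SD difference of that kind was small. A site term is worth having on either reading of the allocation, and it is a change that should be made because it costs almost nothing.

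**What to change.** - **Randomization.** State that H/L allocation uses permuted blocks within site by *MC1R* risk group, and give the block size. Four lists with 100 per arm in each yield 200 high-risk participants per arm and 800 in total, which agrees with Project Description and Statistics.
- **Aims 1 and 2.** Prespecify site as a fixed covariate in every H/L model, with a site-by-time term and month effects that may differ by site. Report the arm effect by site as a descriptive result.
- **Aim 2 question.** As a minor point, name the recruiting clinic at Ponce for participants enrolled there.

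The cost is at most two further randomisation lists, a few model parameters and one change of survey wording. No extra participants or staff are needed. If allocation has already begun, document the method actually used; the model terms can still be fixed before the data are analysed.

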Participants reporting sun-sensitive phenotypes.

Participants having had a skin examination within the past year.

Exclusion Criteria for our H/L population:

Children under the age of 18

Participant whose medical records or self-report indicate an ethnicity aside from Hispanic.

Participants having had a skin examination within the past year.

Participants with a personal history of melanoma and/or more personal history of more than one SCC and/or BCC.

Primary Outcome of the Study:

Primary outcomes will be measured using an adapted version of a published survey assessing measures of sun exposure and sun protection (Glanz et al. 2008) (see **Appendix**).

For Aims 1 and 2, the 14-item measure for adults (Section A) will be used. Section A is completed by the study participant and elicits responses about his/her own sun protection and skin examination behaviors including: average number of hours spent outside during weekdays and weekend days in the summer; number of red or painful sunburns during the past 12 months; frequency of sun protection behaviors when outside in the summer sun; frequency of intentional tanning; color of untanned skin; and skin examinations by a health professional or by the study participant him/herself or his/her partner.

For Aim 1, the primary outcome of interest is average number of hours spent in the sun per week between 10am – 4pm. This measure will be a weighted average of the first two questions on the survey asking about number of hours spent outside during the hours of 10 to 4 on weekdays (Section A, Q1) and on weekend days (Section A, Q2). We will tailor the timeframe of Q1 and Q2 given in Glanz et al. to fit our Aim and our timeline (Glanz et al. 2008). At baseline the timeframe will be “in the past 12 months”; and for our white, non-Hispanic population at the 6 and 12 month follow-up surveys and

at 3 and 9 month for our H/L population, the timeframe will be “in the past 6 months” for our white, non-Hispanic populations and “in the past 3 months” for our H/L population.

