Study power, Aim 2. We estimate a 20% incidence of having a skin examination within the past 12 months among participants on the placebo arm who received only standard risk and prevention information. We also conservatively estimate study attrition at 20%. Using these estimates, we determined that randomizing 500 participants with high risk *MC1R* variants (250 per study arm) ensures 80% power to detect an odds ratio of at least 1.8 when comparing participants with high risk genotypes who are randomized to intervention to participants with high risk genotypes who are randomized to placebo for the skin examination (yes/no) outcome. These calculations are based on two-sided, alpha=0.05 level tests and vary the proportion of skin examinations in the placebo group from 15-36% to be consistent with the range of possible values noted in the published literature.

Because we do not know the proportion of study participants who will have children 10 years of age or younger, we do not report study power for Aim 3 and consider this aim as exploratory at this time.

For our H/L populations the total number of participants, 400 with high risk *MC1R* genotypes (200 of whom will be recruited locally and 200 recruited in PR) required to participate in this study was based upon the power calculations below.

Hispanic/Latino study population

For our H/L populations the total number of participants, 400 with high risk *MC1R* genotypes (200 of whom will be recruited locally and 200 recruited in PR) required to participate in this study based upon the power calculations below.

Study power, Aim 1. Randomizing 400 participants with high risk *MC1R* variants (200 each to the intervention and control arm) ensures 80% power to detect mean differences in hours of sun exposure comparable to a small-medium effect size (Cohen's $d=30$),

when comparing participants with high-risk genotypes to intervention versus participants with high-risk genotypes randomized to control.

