Study power, Aim 2. We estimate a 20% incidence of having a skin examination with the past 9 months among control participants, with a range of 15% to 35%, and estimate study attrition of 20%. Using these estimates, we determined that randomizing 400 participants with high-risk *MC1R* variants (200 per study arm) ensures 80% power to detect an odds ratio of at least 1.95 to 1.73 when comparing participants with high-risk genotypes randomized to intervention versus those randomized to control for the skin examination (yes/no) outcome.

General approach. All analyses will be done within SAS, version 9 or later, primarily using PROC UNIVARIATE, FREQ and GENMOD. In the primary analyses, we will use an intention-to-treat (ITT) approach in which participants are analyzed in their randomized conditions regardless of the number of interventions or number of follow-up assessments they complete. Two-sided tests will be used for all hypotheses. We will assess the data for missing and out-of-range values with basic statistical procedures, including univariate statistics and graphs (histograms, box and whisker plots, scatter plots, and Q-Q plots). We will investigate data quality and integrity before any statistical modeling to ensure unbiased estimation.

The primary aim of this proposal is to test for significant ITT differences in the proportion of study subjects participating in skin prevention behaviors over the 12-month follow-up period by comparing those who receive a risk and prevention education intervention that includes feedback of *MC1R* genotype to those who receive a risk and prevention education session that includes only standard information. Our two primary outcomes of interests are (1) the average hours per week (weekdays and weekend) spent outside between 10am – 4pm; and (2) the completion of a full body skin examination for skin cancer (yes/no) by self, partner or clinician.

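### In the white, non-Hispanic cohort no Aim 2 outcome covers the 12 months in which the aim and the power are stated; the month-12 response covers months 6–12 only and can understate an early effect

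*Combined protocol and SAP*

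**What the plan says.** Under Primary Outcome of the Study, the Aim 2 outcome is yes if the participant reports an examination by a clinician, by oneself or by a partner. For this cohort the follow-up look-back is the same at both surveys: "at the 6 and 12 month follow-up surveys, the timeframe will be “in the past 6 months” for our white, non-Hispanic population". The outcome is then fixed as "this outcome is operationally a binary response (e.g., yes/no in the past 6 months (for our white, non-Hispanic participants". The two surveys therefore cover months 0–6 and months 6–12, without overlap. Those who answer yes are also asked "the month and year of examination and whether the examination occurred at the Morsani Family Medicine or General Internal Medicine clinics"; those who answer no are not.

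Elsewhere the period is 12 months:

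- STATISTICS, General approach, states the primary aim as a difference in the "proportion of study subjects participating in skin prevention behaviors over the 12-month follow-up period".
- Study power, Aim 2: "We estimate a 20% incidence of having a skin examination within the past 12 months among participants on the placebo arm".
- The baseline item: "at baseline the timeframe will be “in the past 12 months".
- Exclusion Criteria: "Participants having had a skin examination within the past year".

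The objectives name short-term (6-month) and long-term (12-month) efficacy. They do not say whether the latter means examined by month 12 or examined again in months 6–12. STATISTICS, Aim 2, puts times 0, 6 and 12 months into one logistic GEE with the arm-by-time interaction as the main test.

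**The concern.** No planned outcome measures the quantity that the aim describes and the power calculation uses, which is the proportion examined within 12 months. The nearest candidate, the month-12 response, drops examinations in months 0–6 that are not repeated.

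This matters because the intervention is delivered early. The packet, the telephone session and the first summary letter all come at the start, and the second letter goes out only after the final questionnaire. If feedback prompts early examinations, the arm that responds more has more people whose single examination falls outside the second window. The month-12 contrast can then be weaker than the 12-month effect. Since the main test concerns change over time between arms, a fall in the contrast from month 6 to month 12 also enters that test.

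**Working it through.** **Inputs from the plan (Study power, Aim 2):** control 20% within 12 months; odds ratio 1.8; 250 per arm in the high-risk stratum; 20% attrition, leaving 0.80 × 250 = 200; two-sided alpha 0.05. The intervention proportion is 0.20 × 1.8 / (0.80 + 0.20 × 1.8) = 0.36 / 1.16 = 0.3103.

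**The plan's own figure.** For two proportions with pooled variance under the null, power = Φ{[|p₂ − p₁|√n − 1.96√(2p̄(1 − p̄))] / √(p₁(1 − p₁) + p₂(1 − p₂))}.

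- n = 250: (0.1103 × 15.81 − 1.96 × 0.6165) / 0.6116 = 0.877, so power is 81.0%. The stated 80% is reproduced, with the 12-month rate and no loss.
- n = 200: power is 71.8%.
- The plan does not say how attrition and repeated measures entered. Two averaged waves at 200 per arm with an assumed correlation of about 0.6 give an effective n of 2 × 200 / 1.6 = 250, and again 81%.

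**Power for one 6-month window.** Assume a steady control rate and no repeats. Then 20% per year becomes 10.0% per window (even split), or 1 − √0.80 = 10.6% (constant rate). For odds ratio 1.8:

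| Control rate per window | Power, 250 per arm | Power, 200 per arm |
|---|---|---|
| 10.0% | 59% | 50% |
| 10.6% | 61% | 52% |

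The plan varies the 12-month control proportion ("These calculations are based on two-sided, alpha=0.05 level tests and vary the proportion of skin examinations in the placebo group from 15-36"%), but that range does not address the change of window.

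**Month-12 contrast when the 12-month effect is as planned.** Hold the 12-month proportions at I = 0.3103 and C = 0.20. Three assumptions are not in the documents: control first examinations split evenly between windows; a share s of intervention first examinations falls in months 0–6; and a proportion r of those examined early, in either arm, is examined again in months 6–12.

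- Month 6: intervention sI; control 0.5C = 0.10.
- Month 12: intervention (1 − s)I + r·s·I; control 0.10 + 0.10r.

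Example, s = 0.75 and r = 0: month 12 is 0.25 × 0.3103 = 0.0776 versus 0.10, so the odds ratio is (0.0776/0.9224) / (0.10/0.90) = 0.76. Example, s = 0.90 and r = 0.50: 0.0310 + 0.1397 = 0.1707 versus 0.15, odds ratio 1.17.

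| Early share s | Month-6 OR | Month-12 OR, r = 0 | r = 0.25 | r = 0.50 | r = 1 |
|---|---|---|---|---|---|
| 50% | 1.65 | 1.65 | 1.68 | 1.72 | 1.80 |
| 60% | 2.06 | 1.28 | 1.44 | 1.57 | 1.80 |
| 68% | 2.41 | 0.99 | 1.26 | 1.46 | 1.80 |
| 75% | 2.73 | 0.76 | 1.10 | 1.36 | 1.80 |
| 90% | 3.49 | 0.29 | 0.79 | 1.17 | 1.80 |

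With no repeats the month-12 odds ratio is exactly 1.00 when (1 − s) × 0.3103 = 0.10, that is s = 67.8%. The 1.65 at an even split is only the odds-ratio scale: the risk ratio is 1.55 in the window (0.155/0.10) and over 12 months (0.310/0.20).

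**The case against.** Several points on the other side stand.

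- A reader might infer that anyone examined early is scored as a failure at month 12. That holds only if no clinician, self or partner examination follows in months 6–12, and self-examination needs no visit. At 50% repetition there is no reversal in the table.
- A reader might infer that the early examination is lost. It is not: it is a yes at month 6 in the same GEE, and a 0–12 month indicator can be built from the two windows when both surveys are returned.
- Contiguous windows are a reasonable way to study sustained behaviour. The objectives list 6 and 12 months separately, and the RISKS section ties benefit to behaviour that is kept up. If continued examining is the target, a null in months 6–12 is a true finding, and replacing the primary outcome outright would be a preference about the estimand.
- It is tempting to place 20% versus 31% in months 0–6 and apply 20% again to the unexamined. That treats the plan's 12-month rate as a 6-month rate and implies 0.20 + 0.80 × 0.20 = 36% of controls by month 12, against the planned 20%.

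The wording of the aim could also be read loosely as describing a repeated-measures analysis. That does not settle the matter: the power input is explicitly a 12-month incidence, and the plan never states which long-term quantity it targets.

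**Conclusion.** The mismatch is certain from the text: 12 months for the aim, power, baseline and eligibility, and 6 months for each follow-up response, with no outcome that joins them. Its effect on the month-12 contrast is conditional. Against a true 12-month odds ratio of 1.8, that contrast is attenuated when uptake is early. It is null or reversed only with strong front-loading and few repeats: about 68% early with no repeats, or between 75% and 90% early with 25% repeating. The documents give neither a timing split nor a repeat rate, so they do not support the reading that the long-term result will be null or reversed whenever the intervention works. Nor do they show that the window outcomes are wrong and must go. What they support is that the 12-month question as posed and powered has no matching outcome, and that the stated power does not carry over to a single 6-month window.

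**What to change.** For the white, non-Hispanic cohort:

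1. Prespecify a cumulative 0–12 month outcome, yes at either the 6- or the 12-month survey, as the 12-month comparison that answers the aim. Analyse it as a single arm comparison by logistic regression, outside the 0/6/12-month arm-by-time GEE, because a cumulative yes cannot revert to no.
2. Keep the months 0–6 and 6–12 responses in the GEE and label the second as continued or repeat examination.
3. At month 12 ask every participant the same item covering the whole follow-up, so that recall length does not depend on a missed 6-month survey. State in advance which answer governs if it disagrees with the 6-month survey.
4. Treat no at 6 months with a missing 12-month survey as missing. Because a known yes is kept while such a no is not, add a sensitivity analysis in month-12 responders or by imputation.
5. State that the Study power, Aim 2 figure refers to the 12-month outcome, say how the 20% attrition enters it, and give the single-window power beside it.

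The cost is SAP wording and one survey item, with no new patients or visits. The downsides are longer recall and an outcome that cannot by itself show a sustained effect, which is why the window outcomes stay. The same derivation does not carry over to the Hispanic/Latino cohort: its month-9 survey looks back 3 months, so months 3–6 fall in neither window.
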